### Don't know/Not sure

(2): s114-20.

The last question is about the time you spent **sitting** on weekdays during the **last 7 days**. Include time spent at work, at home, while doing course work and during leisure time. This may include time spent sitting at a desk, visiting friends, reading, or sitting or lying down to watch television.

9.	During the last 7 days, how much time did you spend sitting on a week day?	
	hours per day	
	minutes per day	
	Don't know/Not sure	

Items in green are not part of the IPAQ, but were added for purposes of the current study.

Booth, M.L. (2000). Assessment of Physical Activity: An International Perspective. Research Quarterly for Exercise and Sport, 71

## **Appendix H**

### Weekly email/SurveyMonkey

Thank you for participating in "Assessing the Impact of Internet-Guided Pilates Training on People with Hypermobility."

We hope you are continuing to do the Pilates exercises, but remember that you should only do what you feel is appropriate for you. As long as you continue to respond to the questionnaires, you are still an active research subject, independent of whether or how much Pilates exercise you do.

You may contact [name] if you have questions about the Pilates program, but please do not share information regarding your response to the research questions in SurveyMonkey, as [name] is "blinded" to the research data (for scientific validity and to protect your private information, she is not supposed to know how individual subjects respond to the research questions). Please do not Reply to this email. If you would like to contact [name] with questions about the Pilates program, please email her directly at: [contact].

Please click on the following link to go to SurveyMonkey, where we will ask you some questions about your participation. These questions will take 10-30 minutes, depending on how much you would like to share about your experience.

SL	RVEY M	MONKEY CONTENT FOR WEEKLY FOLLOW-UP EMAILS (not included in the emails)  The 3 first letters of the month (in English) of your MOTHER'S birthday (e.g., SEP)  YOUR 2-digit birthday date (e.g., Ø8 for May, 8th)  The first letter of YOUR MIDDLE NAME; enter X if you do not know or have a middle name (e.g. M for Mary)				
	•	The total number of OLDER SIBLINGS you have, including living, deceased, and half (e.g., 0 if you are an only child; enter 9 if you have 10 or more siblings)  In this example, your identification code would be SEP08M0 (SEPØ8MØ)				
ра	ticipatio	ng questions are part of the research data collection, and will not be analyzed until your n is complete. Feel free to email [name] ( [contact] ) if you have about the Pilates activities, and would like a response.				
PΙε	ase ans	wer questions 1 and 2 every week.				
1. 2.	you think is due to the Pilates exercises? Yes / No a. If so, briefly describe. [narrative response]					
rea	son, pl	e increased pain or other symptoms, either due to the Pilates exercises or any other ease modify or omit any or all Pilates exercises that do not feel safe to do and contact h care provider as appropriate.				
3.		of the following are challenges that make it difficult for you to do the Pilates exercises, or to m as much as you otherwise would? (select all that apply)				
	a.	I do not enjoy the Pilates exercises				
	b.	I enjoy different types of exercise more				
	C.	The Pilates exercises are too uncomfortable				
	d.	The Pilates exercises are too difficult				
	e.	Not enough time to exercise, or difficulty scheduling time				
	f.	Personal issues came up and I was unable to do the exercises				
	g.	I hurt too much				
	h.	I am too fatigued to do Pilates				
	i.	I have symptoms (other than pain or fatigue) that limit my participation (e.g., dizziness,				
		stomach problems, etc.)				
	i.	I am not physically able to do these exercises now				

You are invited to answer the remaining questions if you would like to share your thoughts. To keep our research data confidential, please do not include any personal identifying information in your responses.

- 4. What challenges do you experience in doing the Pilates exercises? These may include challenges with specific exercises, understanding instructions, scheduling time, discomfort, or any other aspect of following this program. [narrative response]
- 5. How are the exercises and activities in the Pilates course affecting you physically and/or psychologically? [narrative response]
- 6. What do you enjoy or like most about the Pilates program? [narrative response]

k. I am afraid the Pilates exercises might harm mel. I am afraid that any type of exercise might harm me

7. What other comments do you have about participating in this on-line Pilates training? [narrative response]

# Thank you for participating in this research

### Appendix I.1: Email requesting Follow-Up Health History after 8 weeks of Pilates and at 6 month follow-up.

Thank you for participating in "Assessing the Impact of Internet-Guided Pilates Training on People with Hypermobility."

We hope you are continuing to do the Pilates exercises, but remember that you should only do what you feel is appropriate for you. All subjects have access to the Pilates videos during the 8 initial weeks of the study and 6 months of follow up, whether or not you do the Pilates exercises. Subjects who complete the 8 week and 6 month follow-up surveys will also be given permanent access to the on line Pilates modules.

You may contact [name] if you have questions about the Pilates program, but please do not share information regarding your response to the research questions in SurveyMonkey, as [name] is "blinded" to the research data (for scientific validity and to protect your private information, she is not supposed to know how individual subjects respond to the research questions). Please do not Reply to this email. If you would like to contact [name] with questions about the Pilates program, please email her directly at: [contact].

Append	lix I.2: Foll	ow-Up Health History after 8 weeks of Pilates and at 6 month follow-up.  The 3 first letters of the month (in English) of your MOTHER'S birthday (e.g., SEP)					
		YOUR 2-digit birthday date (e.g., Ø8 for May, 8th) The first letter of YOUR MIDDLE NAME; enter X if you do not know or have a middle name (e.g. M for Mary) The total number of OLDER SIBLINGS you have, including living, deceased, and half (e.g., 0 if you are an only child enter 9 if you have 10 or more siblings)					
	• In this	s example, the identification code would be SEP08M0 (SEPØ8MØ)					
Your 7-ch	naracter ID C						
-	=	ons will either state "8 weeks" or "6 months" depending on which time the survey is done] Did your health care program change significantly during the course of this research?					
2.		Did you have any increased pain or problems in the past 8 weeks (6 months), beyond eness from doing new exercises, that you think was due to the Pilates exercises?					
	a.	If so, briefly describe.(narrative)					
3.		Did you have any injuries or increase in symptoms during the past 8 weeks (6 months) ed to the Pilates program, that has affected your ability to do the Pilates exercises					
4.	How ma	How many total minutes of any Pilates exercises do you currently do in a typical week?					
5.		f the following reasons explain why you do not do Pilates exercises, or why you do not as much as you otherwise would? (select all that apply)					
	a.	I did not enjoy the Pilates exercises					
	b.	I enjoy different types of exercise more					
	c.	The Pilates exercises were too uncomfortable					
	d.	The Pilates exercises were too difficult					
	e.	Not enough time to exercise, or difficulty scheduling time					
	f.	Personal issues came up and I was unable to do the exercises					
	g.	I hurt too much					
	h.	I am too fatigued to do Pilates					
		I have symptoms (other than pain or fatigue) that limit my participation (e.g., dizziness stomach problems, etc.)					
	j.	I am not physically able to do these exercises now					
	k.	I am afraid the Pilates exercises might harm me					
	1.	I am afraid that any type of exercise might harm me					
	m.	Other:					
6.	•	nave any comments about reasons why it was difficult or not possible for you to do the or any other aspect of following this program. (narrative)					
7.	Please r	ate how helpful you feel this Pilates program has been for you, overall: (drag bar)					
No	t helpful	at all 0 1 2 3 4 5 6 7 8 9 10 Extremely helpful					
8.		ve the exercises and activities in the Pilates course affected you physically and/or ogically (if they have)? (narrative)					
9.	What di	What did you enjoy or like most about the Pilates program? (narrative)					
10.		Would you recommend this Pilates program, "Strengthen Your Hypermobile Core" to who are hypermobile?					
	Why or why not? (narrative)						
11.	What ot	her comments do you have about participating in this on-line Pilates training?					

(narrative)

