sessions and, if so, why. We will also ask if they have any comments about the modules or about their experience. We will also ask about any changes in pain, either related to the Pilates practice, or unrelated. The contact email will also remind them that they can contact one of the PI (JD) if they have questions or problems with the Pilates, or (LR) if they have any questions about research participation.

At the end of 8 weeks, subjects will be asked to repeat the initial questionnaires on SurveyMonkey, and comment on their experience doing the Pilates. This is likely to take about 60 minutes. Subjects will continue to have access to the Pilates modules and we will encourage them to continue using the modules. We will track whether individuals do access the modules over the next 6 months.

Six months after subjects complete the 8 week exercise session, we will contact each subject again and ask him/her to repeat the initial questionnaires on SurveyMonkey, and again comment on whether they felt the Pilates was helpful.

We will also include an 8-week wait-list group constructed from subjects asking to participate after we have already recruited 225 subjects. This wait list is primarily because we do not want to be so overwhelmed by participants that we cannot manage them effectively (responding to questions about the Pilates, sending out follow-up surveys, etc.). Also, a wait-list group would provide a control group (albeit not randomly selected). All participants who do not start in the initial group will be asked if they still want to participate in a wait-list group; if they do, we will contact them 8 weeks after their initial surveys were completed, ask them to repeat the surveys, then start them in the Pilates program.

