### **b. Measurement tools.** (Attach questionnaires and surveys as labeled appendices.)

- Demographic questionnaire (see Appendix C)
- \* The Bristol Impact of Hypermobility questionnaire (BloH) will be used to assess changes in pain, fatigue, self-efficacy and function.(Palmer, 2017. see Appendix D)
- The Revised Body Awareness Rating Questionnaire (R-BARQ). 12 questions. (Dragesund, 2018, Appendix E).
- The Tampa Scale of Kinesiophobia (TSK, 11 item version) will be used to assess kinesiophobia. (Woby, 2005. See Appendix F)
- The International Physical Activity Questionnaires (IPAQ) Short Form is a validated survey assessing physical activity during work, sport, and leisure time; this will be used to monitor activity level.(Booth, 2000. See Appendix G)
- Weekly Email questions for qualitative information and adverse event reporting. (Appendix H)
- Post-intervention questions for 8 weeks and 6 months (Appendix I)

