# c. Address how subjects will be monitored for adverse effects and what remediation is offered.

The research will include a weekly email to touch base with each subject, reminding them to participate at the level they are comfortable (doing any, all, or no Pilates). Subjects will be asked about increased pain or problems, beyond mild soreness from doing new exercises, that they think may be due to the Pilates exercises, as that is important data. Subjects will be reminded: "If you have increased pain or problems, either due to the Pilates exercises or any other reason, please modify or omit any or all Pilates exercises that do not feel safe to do and contact your health care provider as appropriate." However, no remediation will be offered or provided.

Subjects

- d. Does the data to be collected relate to illegal activities? If so explain. NA
- **e.** Rate risk level. Check the most appropriate risk level below. (Minimal risk means that the probability and magnitude of harm or discomfort anticipated in the research are not greater in and of themselves than those ordinarily encountered in daily life or during the performance of routine physical or psychological examinations or tests.)

The research involves no more than minimal risk to subjects.
The research involves more than minimal risk to subjects but the risk(s) represents a minor increase
over minimal risk, or
The research involves more than minimal risk to subjects and the risk(s) represents more than a minor
increase over minimal risk

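### The 8-week and 6-month form misses harms that are neither blamed on Pilates nor limiting it, and sections 6a and 7c differ on how widely to ask

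*Combined protocol and SAP*

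**What the plan says.** Four places bear on how harm is recorded.

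- **Section 6a (procedure, weekly email)** sets a broad scope: "We will also ask about any changes in pain, either related to the Pilates practice, or unrelated".
- **Section 6b (measurement tools)** makes the weekly survey the adverse-event instrument: "Weekly Email questions for qualitative information and adverse event reporting".
- **Section 7c (monitoring for adverse effects)** describes a narrower scope. The question put to subjects concerns "increased pain or problems, beyond mild soreness from doing new exercises, that they think may be due to the Pilates exercises".
- **Appendix I.2 (form used at 8 weeks and at 6 months)** has two harm items. Question 2 asks about increased pain or problems beyond mild soreness "that you think was due to the Pilates exercises". Question 3 begins "Did you have any injuries or increase in symptoms during the past 8 weeks (6 months" and ends with the condition "that has affected your ability to do the Pilates exercises". Between these, one word is cut to its last letters. The sensible reading is that the question concerns events unrelated to the program, but that is an inference.

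In Appendix H (the weekly form), the wording of question 1 and the start of question 2 are not legible. What can be read is "you think is due to the Pilates exercises? Yes / No a. If so, briefly describe. [narrative response".

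The analysis list in section 6e contains no adverse-event analysis.

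**The concern.** Both legible harm items on the follow-up form apply a filter before anything is recorded. One filter is the subject's own view of cause; the other is whether Pilates was affected. In this population the first filter is hard to apply. Section 2 describes pain, balance problems, reduced proprioception and autonomic disorders as common, and the exclusion criteria in section 4b expressly let in people with their typical flares. Such subjects are poorly placed to say whether a given flare or slipped joint came from the exercises or would have happened anyway. They also know that they are doing Pilates, so the attributed count depends partly on what they believe about it.

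A filter at the point of asking cannot be undone in the analysis. If the study reported few or no adverse effects, part of that result could come from the wording of the questions.

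**Working it through.** No arithmetic in the plan bears on this point: the documents give no adverse-event rate, harm threshold or safety sample size. The check is a comparison of the texts, followed by a sort of events by how the form would treat them.

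**1. Scope promised against scope described.** Section 6a covers changes in pain whether related or unrelated. Section 7c mentions only problems the subject thinks may be due to Pilates. Both concern the weekly contact, so this is a like-for-like comparison, and the two differ in scope.

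**2. What Appendix I.2 captures**, taking question 3 to mean unrelated events:

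| Event | Limits Pilates | Does not limit Pilates |
|---|---|---|
| Attributed to Pilates | Question 2 | Question 2 |
| Not attributed to Pilates | Question 3 | No harm item |

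One cell of the four is empty. For example, a shoulder slips out in week 3. The subject regards this as usual for hypermobility and carries on with the exercises. The answers at week 8 are No to question 2 and No to question 3.

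**3. Whether other items fill the empty cell.**

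- *BIoH.* It asks, without reference to Pilates, about pain by site, unexpected pain, giving way, loss of balance and joints slipping out of place. The recall period is 7 days. Against the 8-week intervention that is 7 / (8 × 7) = 7 / 56 = 12.5% of the period. Against six months, taken as about 182 days, it is 7 / 182 = 3.8%. The items are ratings that feed an outcome score and do not record events. The week-3 shoulder falls outside the window.
- *Barrier lists* (Appendix H question 3, Appendix I.2 question 5). These ask why the subject does less Pilates, so they share the limitation filter.
- *Narrative items.* They may pick up an event by chance, but those in the weekly form are optional, and section 6e routes the email narratives to content analysis, not to a harm count.
- *Weekly question 1.* It cannot be read. It may ask about unrelated pain. If it does, it would help during the 8 weeks; for the following six months section 6a describes module tracking and one further survey, with no weekly contact.

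**4. Comparator.** Section 6a has the wait-list group repeat the initial surveys after 8 weeks. No harm question for the waiting period is described, so there is no background rate of injuries or flares to set beside the Pilates period.

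**5. Size.** For N subjects with at most one event each, the expected number missed on the form is N × P(event) × P(not attributed, given an event) × P(not limiting, given an event not attributed). The documents supply none of these three probabilities, so no figure can be derived.

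**The case against.** The strongest objection is that the broad promise and the follow-up form are different instruments. Section 6a's sentence is about the weekly survey and promises nothing about Appendix I.2. The form that would test the promise is Appendix H, and its question 1 is lost from the text. This stands. A reader might infer that the weekly form breaks the promise; the documents do not show that. The comparison that can be made is between sections 6a and 7c, and Appendix I.2 is a separate gap.

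Section 7c also does not say that attributed problems are the only ones asked about, and its reminder to subjects mentions problems from any other reason. A short summary need not contradict a fuller one. This is fair as far as it goes. However, the reminder tells subjects what to do and does not collect data, and 7c is where a reader looks for the monitoring rule.

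A reader might also infer that all injuries and flares not blamed on Pilates go uncounted. That is too broad: question 3 appears to count those that affected Pilates. Nor is it right that nothing at all would show. Worsening from any cause can appear in the BIoH, whose 8-week change is compared with the wait-list group. What the BIoH cannot supply is a count of events over the period.

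Finally, this is a pilot of gentle exercise, safety is not among the objectives in section 3, and an all-cause count in a flaring population is hard to read. The last part stands and shapes the fix: an all-cause count needs a comparator.

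**Conclusion.** The point holds in a limited form. Sections 6a and 7c differ in the scope of the weekly questioning and should be reconciled. On the 8-week and 6-month form, events that are neither attributed to Pilates nor limiting it are not captured as harms. The gap matters most for the six-month follow-up, where that form carries the only harm questions the plan describes.

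This rests on reading the cut word in question 3 as *unrelated*. If that reading is wrong, the set of events captured by question 3 changes. No claim is made about the content of weekly question 1. The number of events missed is unknown: any figure would rest on assumed event and attribution rates, and would be too high if it ignored question 3. This is an inexpensive improvement to the harm data and does not affect the planned efficacy analyses.

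**What to change.** 1. Bring sections 6a and 7c into line, stating one scope for the weekly questioning, and check that Appendix H matches it.
2. Replace Appendix I.2 questions 2 and 3, and the item described in section 7c, with one unfiltered question: any injury, dislocation or subluxation, fall, or increase in pain or symptoms beyond mild soreness during the period (yes/no, describe). Follow it with two sub-items: whether the subject thinks it was related to Pilates (yes/no/unsure), and whether it limited Pilates.
3. Put the same unfiltered question, without the Pilates sub-items, in the wait-list group's 8-week repeat survey, so that the all-cause count has a comparator, albeit a non-randomised one.
4. Add to section 6e a descriptive report of both the all-cause and the attributed counts.

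The cost is rewording existing items and adding one question to a survey the wait-list group already completes, with no extra contact. The attributed count is kept. The downside is that more background flares will be reported, so the all-cause count will look less favourable and must be read alongside the wait-list figure and the sub-items.

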# Thank you for participating in this research
